1. TITLE

Older Adult Safety in Surgery (OASIS) IV

2. EXTERNAL IRB REVIEW HISTORY*

N/A

3. PRIOR APPROVALS:

N/A

4. OBJECTIVES*

Surgery is a life-saving procedure for patients with cancer and can enhance quality of life for patients with intractable abdominal or thoracic disease. Although most patients tolerate the procedure well, frail older adults have as much as a threefold increase in the risk of adverse outcomes after surgery.¹ In response to this risk, some investigators^{2,4} have studied preoperative exercise interventions (a.k.a. pre-habilitation).

So far, pre-habilitation studies^{2,4} have shown improvement in endurance but not a reduction in adverse outcomes such as medical complications, discharge to nursing home, or readmission. Potential explanations are that these studies were too small to show a difference but also they did not focus on frail older adults who could benefit most from prehabilitation. A final explanation is that they relied on clinic visits with physical therapists or kinesiologists which can add to the stress and cost of surgery for patients already burdened with appointments in the short preoperative period.

A home walking prescription self-monitored with a modern pedometer (e.g. Fitbit type wristband) provides a convenient and cost-effective method for prehabilitation. Despite the apparent advantages of a home walking program, no one has demonstrated that such a program can reduce the incidence of adverse outcomes or improve physical status assessments such as endurance, balance, gait speed, strength, and self-reported function. If our investigative group establishes that a walking prescription supported by pedometer improves these assessments, we would be in a favorable position to embark on a larger study to demonstrate a reduction in adverse clinical outcomes.

There are other data that would be helpful to collect prior to embarking on the larger study. These include the role of varying duration of the walking regimen. Given the rush to proceed with surgery in anxious patients, it would be important to know how well the intervention works over the range of times available and if there exists a threshold of duration (e.g. 1-2 weeks) below which a walking prescription would have no effect.

Additionally, it would be important to analyze step counts from the pedometer and the percentage of days in which individual patients achieved prescribed targets. This would permit assessing whether any improvements in physical status resulted from the walking intervention. Conversely, if there is no improvement in physical status assessments, we could diagnose if nonadherence with the walking prescription was the reason. Finally, it would be helpful in guiding future research to calculate the time and cost required to recruit eligible patients as well as to assess patient satisfaction with the walking prescription.

INVESTIGATOR STUDY PLAN - REQUIRED

We therefore propose a study of 400 older adults scheduled for surgery with the following aims which will prepare us to conduct a larger trial focused on clinical outcomes.

Aim 1: To assess the impact of a walking prescription intervention on outcomes of endurance, balance, gait speed, strength, and self-reported function in patients with frailty.

Aim 1a: To estimate improvement in outcomes as a function of duration of the walking intervention.

Aim 1b: To re-estimate the effect of the intervention adjusting for the percentage of days each patient met his/her walking goal.

Aim 1c: To measure patient satisfaction with the walking intervention.

Aim 2: To measure the average time and cost required to recruit and follow up each patient.

Aim 3: Postoperative outcomes: we may also measure several postoperative outcomes

Change in six-minute walk distance from baseline

The number of steps per day in the hospital

Time to 100 steps at the day of discharge.

Discharge to skilled nursing facility

Length of stay

Thirty-day outcomes including serious complication, readmission, and death

Aim 4: Measure the performance of Edmonton frailty score for predicting 30 day outcomes including serious complication, readmission, death.

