of 17) which has been linked with frailty, we will invite to participate in this study to assess preoperative walking as described further below. For those with score of 4 or below, we will not require any further participation apart from the six-month interview. For patients for whom consent can be obtained at the same visit as patient surgical consultation, we will proceed with the baseline assessment as described below. For patients for whom consent cannot be obtained right away or who prefer to come back at another time, we will schedule a follow-up visit within two weeks of initial visit.

Baseline assessment: The RA will record baseline physical status assessments to establish baseline values. We anticipate this will take approximately 30 minutes in addition to the regular office visit. Included in the baseline assessments will be the 6MWD, the SPPB (See attachment), and the Veteran Rand (VR-12) (see attachment).

We will follow the guidelines set in place by the American Thoracic Society (ATS) for administration of the 6MWD. We will utilize safety precautions such as keeping a chair with wheels at the ready nearby at all times for any patient who becomes dizzy or needs to sit for any reason. The baseline 6MWD will be completed in the hallway of the colorectal surgery office at [name]. This is a very low traffic area but we will also do as much as we can to prevent anyone from walking on the course during use. For later assessments administered in the hospital we will set up temporary cones to ensure that no one walks on the course as the patient is walking. Also per the ATS guidelines, the RA will walk the course prior to the patient, so they can ensure that there are no obstructions on the course that may hinder the patient.

We will also follow the ATS guidelines in regards to instructing and encouraging the patient during the walking test. These instructions are stated as follows:

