Participants may walk steps over the course of a day or in one session. The initial walking prescription will also provide instructions to the participant to increase his/her number of steps each week by 10 to 20%.

A research staff member will then orient the participant to the pedometer

Weekly calls: During the interim between the day of consultation until the day of surgery, a study staff member will make weekly calls to each patient. The calls will provide participants an opportunity to report any symptoms which could warrant stopping the walking regimen and/or seeking urgent medical attention. In addition, we will train the study staff member to troubleshoot any problems setting step count targets or other problems with the pedometer. In cases in which the pedometer fails, we will budget to have additional pedometers available to mail to the patient.

Activity log: we will ask participants to log all of their physical activities-date, activity type, number of minutes. We will submit a copy of the activity log to the irb for approval prior to recruiting randomized participants to complete it.

Control subjects: a study staff member will provide general walking advice with typical warnings about when to stop (e.g., chest pain, breathing difficulty, or fall). Control subjects will receive no other intervention. We will also ask control subjects to log their physical activities.

Preoperative assessment: On the day of preoperative testing, which will usually occur three to five weeks after the baseline measurement, a research staff member or other project staff member will collect the pedometer and record the repeat physical status assessments (6MWD and SPPB). On the day of surgery, we may also place a research grade monitor on patients so as to track their steps while in the hospital.

Hospital period assessment: By the day of discharge, we will collect the research grade monitors and repeat our physical status measurements.

INVESTIGATOR STUDY PLAN - REQUIRED

In order to test the above procedures in the randomized individuals, we will enroll up to 15 patients as test patients. All these patients will undergo screening, baseline assessment/interview, follow-up assessment on day of preoperative testing, in-hospital step tracking and Hospital period assessment.

30 day assessment: Approximately 30 days from day of surgery, at office of surgery clinic, we will repeat our physical status measurements

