12. DATA AND SPECIMEN BANKING*

No specimens are being collected as part of the research. Data will not be banked for use in future research outside of the scope of this study.

13. Data Analysis and Management

Analysis As a first step, we will examine the distributions of all variables using histograms and summary statistics for continuous variables, and frequencies for categorical variables. We will consider transformations to enhance normality where continuous variables demonstrate substantial skew or outliers.

Aim 1: We will calculate the distribution of within-participant change for each of the five physical status measures and assess the average and median change against the minimal clinically important difference (MCID) for each assessment, as well as the percentage of patients with a minimal clinically important difference. In cases where a MCID is not available we will decide among our expert advisory team members the threshold values that indicate some important improvement. In our analysis we will also examine the role of baseline assessment on the amount of improvement by using a generalized linear model for the outcome of change in physical status controlling for baseline assessment.

Aim 1a: In this aim, we will examine the association of duration of time available for the intervention with within-participant change in physical status outcomes, using nonparametric locally-weighted scatterplot smoothing (LOESS) regression.¹⁷ We will rerun our generalized linear model controlling for duration of time available for the intervention, transforming the duration variable if indicated by the LOESS plots, e.g., piecewise linear if a threshold effect is seen.

Aim 1b: Similar to Aim 1a analyses, we will examine the association of percentage of days (of the 30 days available in pedometer memory), the step count target was met with within-participant change in physical status outcomes, again using LOESS plots. We will rerun our generalized linear model controlling for the percentage of days in which the patient met their step count target, transforming the percentage of days if indicated by the LOESS plots.

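### Aim 1a: few patients are likely to have the short durations where a threshold is sought, the threshold form is chosen from the data it is refitted to, and no control contrast is specified

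*Combined protocol and SAP*

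**What the plan says.** Section 4 (Objectives) asks about duration in two ways. The general question is that "it would be important to know how well the intervention works over the range of times available". The specific one is whether there is a "threshold of duration (e.g. 1-2 weeks") under which the prescription would do nothing. Aim 1a itself is worded broadly: "To estimate improvement in outcomes as a function of duration of the walking intervention".

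Section 11 (Preoperative assessment) puts the repeat 6MWD and SPPB on the day of preoperative testing, "which will usually occur three to five weeks after the baseline measurement". For patients who cannot consent at once or prefer to return, the same section says "we will schedule a follow-up visit within two weeks of initial visit". No section assigns durations, sets a quota of short ones, or gives their expected distribution.

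Section 13 (Aim 1a) relates within-participant change to the time available, "using nonparametric locally-weighted scatterplot smoothing (LOESS) regression". It then reruns the generalized linear model controlling for duration, transformed if the plots suggest it, "e.g., piecewise linear if a threshold effect is seen". It states no criterion for seeing a threshold, no knot, no allowance for choosing one, and no arm term. Section 11 randomises patients 1:1 to intervention or control.

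**The concern.** There are three linked weaknesses.

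- **Data.** The example threshold lies below the interval in which most patients will be measured. A statement about one to two weeks would rest on very few patients or on extrapolation.
- **Selection.** The knot is read from a plot and then fitted to the same observations. Standard errors that treat it as fixed ignore the search, so an apparent bend looks better supported than it is.
- **Confounding.** Waiting time is not randomised. Section 4 itself mentions the rush to surgery in anxious patients, so duration may reflect the patient or the disease. Change may also drift with time without any walking prescription. A regression of change on duration that names no control contrast cannot separate these from the effect of a longer prescription.

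Section 4 presents duration as something useful to know before a larger study. A threshold produced by the search, or by who waits longer, would be a poor basis for planning it.

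**Working it through.** The plan gives no calculation for Aim 1a, so there is no figure to reproduce. What follows is illustrative, under stated assumptions.

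**Inputs from the documents.** Usual interval of 3 to 5 weeks (Section 11); example threshold of 1 to 2 weeks (Section 4); 1:1 allocation (Section 11); total of 400 (Sections 4 and 25) or 200 (Section 24), hence 200 or 100 intervention patients if all are randomised.

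**Step 1: how many have two weeks or less?** Assume duration is normal with mean 4 weeks and a share c inside 3 to 5 weeks. Then SD = 1 / z(0.5 + c/2), and P(duration ≤ 2) = Φ((2 − 4)/SD).

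| c (assumed) | SD, weeks | (2 − 4)/SD | P(≤ 2 weeks) | of 100 | of 200 |
|---|---|---|---|---|---|
| 60% | 1/0.842 = 1.188 | −1.68 | 4.6% | 4.6 | 9.2 |
| 70% | 1/1.036 = 0.965 | −2.07 | 1.9% | 1.9 | 3.8 |
| 80% | 1/1.282 = 0.780 | −2.56 | 0.5% | 0.5 | 1.0 |

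A log-normal model with the same share in the window gives fewer: 1.5% at 60% and 0.05% at 80%.

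**Step 2: could a two-week knot be seen?** Assume a true knot at 2 weeks, known in advance, and a gain of 0.5 residual SD between weeks 2 and 4. Simulated power for the slope change at the 5% level, counting data sets with nobody below 2 weeks as non-detections, is:

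- 60% in the window: 6% (n = 100) and 9% (n = 200);
- 80% in the window: 2% and 3%;
- durations spread evenly over 0.5 to 5 weeks, so that (2 − 0.5)/4.5 = 33% lie below 2 weeks: 9% and 17%.

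**Step 3: what does choosing the knot from the data do?** Simulate 3,000 data sets with change unrelated to duration and 80% in the window. Choose the best-fitting of 17 knots between the 10th and 90th percentiles of duration, then test the slope change at a nominal 5% as if that knot had been fixed.

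| | n = 100 | n = 200 |
|---|---|---|
| Data-chosen knot, slope change | 15.5% | 16.0% |
| Data-chosen knot, flat then rising | 11.8% | 10.9% |
| Knot fixed at 4 weeks, slope change | 5.0% | 4.9% |

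The simulation standard error for the first entry is √(0.155 × 0.845/3000) = 0.7 percentage points. With durations uniform over 21 to 35 days and a one-day knot grid, n = 100 gives 17.3% and 11.6%. Allowing for variation between runs, the ranges are about 15% to 17% for a slope change and 11% to 13% for flat then rising.

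**Step 4: is there a control contrast?** The time from baseline to preoperative testing is defined in both arms. Section 13 names only within-participant change, the baseline value and duration for this analysis. The arm-by-duration term, which would ask whether the difference between arms grows with time available, is not there.

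**The case against.** The best defence is that Aim 1a is broader than a threshold search. It asks for improvement as a function of duration, Section 4 speaks first of the range of times available, and one to two weeks is only an example. That stands: estimating the relation over the observed durations is feasible, and a sparse lower tail does not defeat the aim.

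A reader might infer that the trial cannot show a threshold at one to two weeks. The documents do not support this. Section 11 says usually, gives no distribution, and allows some visits to be deferred by up to two weeks, which could shorten the interval if the surgery date does not move. The small percentages also depend on the normal shape. With 80% in the window and equal tails, (100 − 80)/2 = 10% fall below three weeks, and only the assumed shape keeps nearly all of them above two. The supportable statement is that few are likely.

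A reader might also infer that the plan tests the knot it has chosen. Section 13 names no test and no significance level; it controls for duration. LOESS followed by a refit is ordinary exploratory practice, and choosing by eye is not an exhaustive search. The inflation therefore applies only if p-values or intervals from the refitted model are read at face value. However, nothing in Section 13 labels them exploratory.

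Finally, no passage says that a threshold found here would set the lead time in the next trial. That consequence is possible but not stated.

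**Conclusion.** The concern holds in this limited form. Few patients are likely to have two weeks or less: about 0.5% to 5% if 80% to 60% fall within three to five weeks, under an assumed normal distribution. A threshold in that region would be poorly identified. A form chosen from the LOESS plot and refitted to the same patients carries unacknowledged selection: roughly 15% to 17% nominal 5% slope changes when there is none (11% to 13% for flat then rising), against about 5% for a fixed knot. Those rates assume a best-fit search and a face-value reading. The missing control contrast needs no distributional assumption: a duration effect estimated from non-randomised waiting time alone may be biased, although both arms are measured. The conflict between 200 and 400 changes the counts, not the conclusion. These are worthwhile improvements to a secondary analysis and do not undermine the main comparison.

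**What to change.** In Section 13, Aim 1a:

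1. Fix the duration form in advance: a linear term, plus a restricted cubic spline with knots at set percentiles. Alternatively, keep the plot-guided choice, bootstrap the whole selection including the knot, and label any threshold exploratory.
2. Fit arm, duration and arm by duration with the baseline value, using both arms for outcomes measured in both. Read the interaction as the duration effect of interest, remembering that duration itself is not randomised.
3. Report the observed distribution of durations by arm, and make no threshold claim outside the well-populated range.

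A minimum count of short-duration patients is not a useful substitute. The documents give no basis for a number, and Step 2 shows low power for a two-week knot even with a third of patients below it.

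In Section 4, one clause noting that the threshold question is limited to the durations observed would be enough. No new visits, patients or measurements are needed. The price is wider intervals and a narrower threshold claim.

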Interim Analyses: Given the possibility that our walking intervention does not improve our physical status measures, we will perform the Aim 1 analysis after recruitment of each batch of 10 patients. More specifically, we will assess the average and median change against the MCID for each of the five measures. If we have not achieved the MCID for any of the measures after any one batch, we will work with our advisors, particularly [name], to revise our intervention (e.g. intensifying the walking regimen) with the goal of improving physical status more than the MCID of one or more measures by the time of the next interim analysis.

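### Aim 1 has five co-equal outcomes and no primary outcome, multiplicity rule or final success criterion, so its conclusion could rest on whichever measure looks best

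*Combined protocol and SAP*

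**What the plan says.** The combined protocol and SAP sets out Aim 1 in Section 4: "To assess the impact of a walking prescription intervention on outcomes of endurance, balance, gait speed, strength, and self-reported function", in frail patients. The five outcomes stand side by side, and neither Section 4 nor Section 10 ranks them. The hypothesis in Section 5 speaks of physical status as a whole by the time of surgery.

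Section 13 (Aim 1) takes within-participant change in each measure and will "assess the average and median change against the minimal clinically important difference (MCID) for each assessment, as well as the percentage of patients" reaching that difference. No MCID value is given. For measures that lack one, "In cases where a MCID is not available we will decide among our expert advisory team members the threshold values"; no date is set for this. The section then models change with adjustment for baseline. It names no treatment-arm term, test, significance level or visit at which change is taken.

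The only target in the plan is in the Interim Analyses paragraph of Section 13, which applies after each batch of 10 patients. The trigger is "If we have not achieved the MCID for any of the measures after any one batch". The intervention is then to be revised "with the goal of improving physical status more than the MCID of one or more measures by the time of the next interim analysis".

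Section 4 gives the purpose: showing that walking improves these assessments would support a larger study of adverse clinical outcomes.

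**The concern.** When five outcomes rank equally and nothing says what the overall conclusion depends on, that conclusion can be settled after the data are seen. If 6MWD does not move but balance does, or if a mean falls short of its threshold while the median passes, the report could still say that walking improves physical status. A reader could not tell whether that was the planned conclusion or a selected one.

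The open thresholds widen the choice, because a level for important change could be set once the changes are known. What is at stake is the credibility of the Aim 1 conclusion and, through it, the decision to proceed to the larger trial.

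**Working it through.** **Inputs from the documents.** Five outcomes (Section 4); three summaries of each, and no MCID values (Section 13); interim looks after every 10 patients (Section 13); 1:1 randomisation (Section 11). The sample size is 400 in Sections 4, 10 and 25 but 200 in Sections 13 and 24, so the intervention arm is 200 or 100. The plan states no alpha, power, effect size or SD, so it has no error rate to reproduce.

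**Assumptions.** Normal outcomes, equal pairwise correlation ρ, no true change, and an MCID of r standard deviations of change.

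**Illustration A: one two-sided 5% test per measure.**
- Independent outcomes: 1 − 0.95^5 = 22.6%.
- Favourable direction only: 1 − 0.975^5 = 11.9%.
- Simulation at ρ = 0.5: 18.3%, of which 9.1% favourable.
- Simulation at ρ = 0.7: 14.8%, of which 7.4% favourable.

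**Illustration B: the literal rule, observed mean above the MCID.** For one measure the chance is p = 1 − Φ(r√n). For any of five independent measures it is 1 − (1 − p)^5. Example: n = 100 and r = 0.2 give p = 1 − Φ(2.0) = 2.3%, and 1 − 0.97725^5 = 10.9%. Values at ρ = 0.5 are simulated.

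| Patients analysed | MCID (SD of change) | One measure | Any of five, ρ = 0 | Any of five, ρ = 0.5 |
|---|---|---|---|---|
| 10 | 0.5 | 5.7% | 25% | 18% |
| 10 | 0.3 | 17.1% | 61% | 44% |
| 100 | 0.2 | 2.3% | 11% | 8% |
| 100 | 0.3 | 0.14% | 0.7% | 0.6% |
| 200 | 0.2 | 0.23% | 1.2% | 1.0% |

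With 200 patients and r = 0.3 the chance is negligible. If only the five intervention patients expected in a batch of 10 are analysed, the chance at r = 0.3 is 57% (ρ = 0.5) to 76% (ρ = 0). If either the mean or the median may pass, the chance for 5 or 10 patients is 32% to 88% (r = 0.5 to 0.3, ρ = 0 to 0.5); for 100 patients at r = 0.3 it is about 4%. The batch figures apply to the first look, or to looks confined to their own batch. If data accumulate, the chance falls as n grows.

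**A limit of both illustrations.** They assume no true change. Section 13 names only within-participant change, so practice effects or regression to the mean could move a measure past its threshold with no effect of walking. A multiplicity adjustment would not remove that; a comparison of the randomised arms would.

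**The case against.** Much can be said for the plan. It is preparatory work, and Section 5 presents assessment over several dimensions as a deliberate strength. Section 4 refers to the assessments in the plural and does not say that one would be enough. Section 10 mentions baseline differences between intervention and control patients, so a comparison of arms is evidently in mind. Balance, strength and gait speed all come from the SPPB, so independence is the least apt assumption. At final size the literal MCID rule rarely passes by chance unless the MCID is small relative to the SD. All of this stands, and it limits the size of the problem. None of it supplies a final criterion, a primary outcome or fixed thresholds.

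A reader might infer three stronger points that the documents do not support:

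- **That success on any one measure is the plan's declared criterion for Aim 1.** The phrase "improving physical status more than the MCID of one or more measures" states the aim of revising the intervention before the next interim look. The final criterion is missing; it is not set at one of five.
- **That there are 15 tests.** Five measures with three summaries make 15 summaries. Mean, median and responder share describe one distribution, the responder share has no pass mark, and the interim rule does not use it. Treating them as 15 independent 5% tests would give 1 − 0.95^15 = 53.7%, which does not describe this plan.
- **That an inflated effect on the best-looking measure will be used to size the next trial.** Section 4 says that trial concerns clinical outcomes. Nothing says that an Aim 1 effect size will feed into its planning. The supported consequence is an influence on the decision to proceed.

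**Conclusion.** The concern holds in a limited form, and the change should be made. It is certain from the text that Aim 1 has no primary outcome, multiplicity rule, final success criterion or stated MCID values. How often chance alone would produce a favourable finding depends on a rule that the plan does not contain:

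- With an assumed two-sided 5% test per measure, 15% to 23% for at least one false positive and 7% to 12% in walking's favour (correlations 0.7 to 0).
- With means compared to an assumed MCID of 0.2 to 0.3 SD, at most about 11% with 100 patients and about 1% with 200.
- In batches of 10 analysed patients, 18% to 61% (MCID 0.5 to 0.3 SD, correlations 0.5 to 0). There the rule says little about whether the intervention works.

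These figures are illustrations. The main defect is that a selected conclusion could not be told from a planned one.

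**What to change.** 1. Name change in 6MWD from baseline to the preoperative test as the single primary outcome. It already shapes the exclusions (Section 6) and the prescription (Section 11), is repeated before surgery (Section 11), and has a between-group benchmark of 41.6 m in the prehabilitation trial cited in Section 5. Other choices are defensible; what matters is naming one.
2. Base the Aim 1 conclusion on the baseline-adjusted difference between randomised arms with its 95% CI, read against a 6MWD MCID fixed, with its source, before outcome data are examined.
3. Treat the other measures as secondary, either Holm-adjusted or reported as estimates only. Keep median change and responder share as descriptive.
4. Reconcile the preoperative visit in Section 11, which lists 6MWD and SPPB but not the VR-12, with self-reported function being an Aim 1 outcome.
5. Say how 6MWD results from the treadmill alternative in Section 10 will be handled.

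The cost is wording; 6MWD needs no new data collection. The downside is that a benefit seen only in another measure could not carry the main conclusion. Keeping five co-equal outcomes with Bonferroni (0.01 each) would cost more. With power = Φ(d√(n/2) − z), n per arm and d = 0.4 SD, power falls from 81% to 60% at 100 per arm, and from 98% to 92% at 200 per arm. The 200 and 400 totals also need reconciling.
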